10.1 Pre-study Documentation

This study will be conducted in accordance with the ethical principles that have their origin in the Declaration of Helsinki as stated in 21 CFR §312.120(c)(4); consistent with GCP and all applicable regulatory requirements.

Before initiating this trial, the Investigator will have written and dated approval from the Institutional Review Board for the protocol, written informed consent form, subject recruitment procedures (e.g., advertisements), and any other written information to be provided to subjects before any protocol related procedures are performed on any subjects.

The Investigator must comply with the applicable regulations in Title 21 of the Code of Federal Regulations (21 CFR) Parts §50, §54, and §312, GCP/ICH guidelines, and all applicable regulatory requirements. The IRB must comply with the regulations in 21 CFR 56 and applicable regulatory requirements.

10.2 Institutional Review Board Approval

The protocol, the proposed informed consent form, and all forms of participant information related to the study (e.g. advertisements used to recruit participants) will be reviewed and approved by the Committee on Human Research (UCSF's IRB). Prior to obtaining CHR approval, the protocol must be approved by the Helen Diller Family Comprehensive Cancer Center Protocol Review Committee (PRC). The initial protocol and all protocol amendments must be approved by the IRB prior to implementation.

10.3 Informed Consent

All participants must be provided a consent form describing the study with sufficient information for participants to make an informed decision regarding their participation. Participants must sign the IRB-approved informed consent form prior to participation in any study specific procedure. The participant must receive a copy of the signed and dated consent document. The original signed copy of the consent document must be retained in the medical record or research file.

10.4 Changes in the Protocol

Once the protocol has been approved by the UCSF Committee on Human Research (CHR), any changes to the protocol must be documented in the form of an amendment. The amendment must be signed by the Investigator and approved by PRC and the CHR prior to implementation.

If it becomes necessary to alter the protocol to eliminate an immediate hazard to patients, an amendment may be implemented prior to CHR approval. In this circumstance, however, the Investigator must then notify the CHR in writing within five (5) working days after implementation.

10.5 Case Report Forms (CRFs)

The Principal Investigator and/or his/her designee will prepare and maintain adequate and accurate participant case histories with observations and data pertinent to the study. Study specific Case Report Forms (CRFs) will document treatment outcomes for data analysis. Study data will be entered into OnCore® and RedCAP, UCSF's Clinical Trial Management System (CTMS) via standardized CRFs in accordance with the CTMS study calendar, using single data entry with a secure access account. The Clinical Research Coordinator (CRC) will complete the CRFs as soon as possible upon completion of the study visit; the Investigator will review and approve the completed CRFs.

The information collected on CRFs shall be identical to that appearing in original source documents. Source documents will be found in the patient's medical records maintained by UCSF personnel. All source documentation should be kept in separate research folders for each patient.

In accordance with federal regulations, the Investigator is responsible for the accuracy and authenticity of all clinical and laboratory data entered onto CRFs. Each CRF must be reviewed for accuracy by the Investigator, corrected as necessary, and then approved. Alternatively, the Investigator may sign individual, printed CRFs. These signatures attest that the information contained on the CRFs is true and accurate.

All source documentation and CTMS data will be available for review/monitoring by the Data and Safety Monitoring Committee (DSMC) and regulatory agencies.

The Principal Investigator will be responsible for ensuring the accurate capture of study data. At study completion, when the database has been declared to be complete and accurate, the database will be locked. Any changes to the database after that time can only be made by joint written agreement among the Principal Investigator, the Trial Statistician, and the Protocol Project Manager.

Appendix 1. Selected Genetic Polymorphisms

Gene	Polymorphism	Location	Protein	Reference
CYP19A1	(TTTA) _n	Intron 4	Aromatase	Tsuchiya N, et al J of Clin Oncol 2006
CYP19A1	rs1870050 A>C	5 kb upstream	Aromatase	Ross R, et al J of Clin Oncol 2008
HSD3B1	rs1856888 A>G	13 kb upstream	HSD	Ross R, et al J of Clin Oncol 2008
HSD17B4	rs7737181 C>G	Intron	HSD	Ross R, et al. J of Clin Oncol 2008
SLCO1B3	334 T>G	Exon 3	OATP	Hamada A, et al. Clin Cancer Res 2008
SLCO1B3	699 G>A	Exon 6	OATP	Hamada A, et al. Clin Cancer Res 2008
SLCO2B1	rs12422149 A>G	Exon 7	OATP	Yang M, et al. J of Clin Oncol 2011
SLCO2B1	rs1789693	Intron 7	OATP	Yang M, et al. J of Clin Oncol 2011
SLCO2B1	rs1077858	Intron 8	OATP	Yang M, et al. J of Clin Oncol 2011
AR	(CAG) _n	Exon 1 (NTD)	Androgen Receptor	Stanford J, et al. Cancer Res 1997
AR	(GGC) _n	Exon 1 (NTD)	Androgen Receptor	Stanford J, et al. Cancer Res 1997
AR	rs17302090	Promoter	Androgen Receptor	Lindstrom et al Clin Cancer Res 2007

[figure not shown]
Appendix 2. Quality of Life Questionnaires

SF-12®:

SF-12®:

SF-12® Cont'd:

EPIC-26:

1. Over the past 4 weeks, how often have you leaked urine?

- More than once a day..... 1
- About once a day..... 2
- More than once a week..... 3 (Circle one number)
- About once a week..... 4
- Rarely or never..... 5

2. Which of the following best describes your urinary control during the last 4 weeks?

- No urinary control whatsoever..... 1
- Frequent dribbling..... 2 (Circle one number)
- Occasional dribbling..... 3
- Total control..... 4

3. How many pads or adult diapers per day did you usually use to control leakage during the last 4 weeks?

- None 0
- 1 pad per day..... 1
- 2 pads per day..... 2 (Circle one number)
- 3 or more pads per day..... 3

4. How big a problem, if any, has each of the following been for you during the last 4 weeks?

(Circle one number on each line)

	No Problem	Very Small Problem	Small Problem	Moderate Problem	Big Problem
a. Dripping or leaking urine	0	1	2	3	4
b. Pain or burning on urination.....	0	1	2	3	4
c. Bleeding with urination.....	0	1	2	3	4
d. Weak urine stream or incomplete emptying.....	0	1	2	3	4
e. Need to urinate frequently during the day.....	0	1	2	3	4

5. Overall, how big a problem has your urinary function been for you during the last 4 weeks?

- No problem..... 1
- Very small problem..... 2
- Small problem..... 3 (Circle one number)
- Moderate problem..... 4
- Big problem..... 5

6. How big a problem, if any, has each of the following been for you? (Circle one number on each line)

	No Problem	Very Small Problem	Small Problem	Moderate Problem	Big Problem
a. Urgency to have a bowel movement	0	1	2	3	4
b. Increased frequency of bowel movements.....	0	1	2	3	4
c. Losing control of your stools.....	0	1	2	3	4
d. Bloody stools	0	1	2	3	4
e. Abdominal/ Pelvic/Rectal pain...	0	1	2	3	4

7. Overall, how big a problem have your bowel habits been for you during the last 4 weeks?

- No problem..... 1
- Very small problem..... 2
- Small problem..... 3 (Circle one number)
- Moderate problem..... 4
- Big problem..... 5

8. How would you rate each of the following during the last 4 weeks? (Circle one number on each line)

	Very Poor to None	Poor	Fair	Good	Very Good
a. Your ability to have an erection?.....	1	2	3	4	5
b. Your ability to reach orgasm (climax)?.....	1	2	3	4	5

9. How would you describe the usual QUALITY of your erections during the last 4 weeks?

- None at all..... 1
- Not firm enough for any sexual activity..... 2
- Firm enough for masturbation and foreplay only..... 3 (Circle one number)
- Firm enough for intercourse..... 4

10. How would you describe the FREQUENCY of your erections during the last 4 weeks?

- I NEVER had an erection when I wanted one..... 1
- I had an erection LESS THAN HALF the time I wanted one..... 2
- I had an erection ABOUT HALF the time I wanted one 3 (Circle one number)
- I had an erection MORE THAN HALF the time I wanted one..... 4
- I had an erection WHENEVER I wanted one..... 5

11. Overall, how would you rate your ability to function sexually during the last 4 weeks?

- Very poor..... 1
 Poor..... 2
 Fair..... 3 (Circle one number)
 Good..... 4
 Very good..... 5

12. Overall, how big a problem has your sexual function or lack of sexual function been for you during the last 4 weeks?

- No problem..... 1
 Very small problem..... 2
 Small problem..... 3 (Circle one number)
 Moderate problem..... 4
 Big problem..... 5

**13. How big a problem during the last 4 weeks, if any, has each of the following been for you?
(Circle one number on each line)**

	No Problem	Very Small Problem	Small Problem	Moderate Problem	Big Problem
a. Hot flashes.....	0	1	2	3	4
b. Breast tenderness/enlargement..	0	1	2	3	4
c. Feeling depressed.....	0	1	2	3	4
d. Lack of energy.....	0	1	2	3	4
e. Change in body weight.....	0	1	2	3	4

Lee Fatigue Scale:

DIRECTIONS: You are asked to place an "X" through these lines to indicate how you are feeling **RIGHT NOW**.
For example, suppose you have not eaten since yesterday. Where would you put the "X" on the line below?

not at all _____ extremely
hungry _____ hungry

You would probably put the "X" closer to the "extremely hungry" end of the line.
This is where I put it:

not at all _____ extremely
hungry _____ hungry

NOW PLEASE COMPLETE THE FOLLOWING ITEMS.

not at all _____ extremely
tired _____ tired

not at all _____ extremely
sleepy _____ sleepy

not at all _____ extremely
drowsy _____ drowsy

not at all _____ extremely
fatigued _____ fatigued

not at all _____ extremely
worn out _____ worn out

not at all _____ extremely
energetic _____ energetic

not at all _____ extremely
active _____ active

not at all _____ extremely
vigorous _____ vigorous

not at all _____ extremely
efficient _____ efficient

not at all _____ extremely
lively _____ lively

not at all _____ totally
bushed _____ bushed

not at all _____ totally
exhausted _____ exhausted

keeping my _____ keeping my
eyes open _____ eyes open
is no effort _____ is a tremendous
at all _____ chore

moving my _____ moving my
body is no _____ body
effort at all _____ is a tremendous
chore

concentrating _____ concentrating
is no effort _____ is a tremendous
at all _____ chore

carrying on _____ carrying on
a conversation _____ a conversation
is no effort _____ is a tremendous
at all _____ chore

I have _____ I have a
absolutely no _____ tremendous
desire to close _____ desire to
my eyes _____ close my eyes

I have _____ I have a
absolutely no _____ tremendous
desire to _____ desire to
lie down _____ lie down

Hot Flash Related Daily Interference Scale (HFRDIS)

Please circle one number to the right of each phrase to describe how much DURING THE PAST WEEK hot flashes have INTERFERED with each aspect of your life. Higher numbers indicate more interference with your life. If you are not experiencing hot flashes or if hot flashes do not interfere with these aspects of your life, please mark zero to the right of each question.

	Do not interfere										Completely interfere
1. Work (work outside the home and housework)	0	1	2	3	4	5	6	7	8	9	10
2. Social activities (time spent with family, friends, etc.)	0	1	2	3	4	5	6	7	8	9	10
3. Leisure activities (time spent relaxing, doing hobbies, etc.)	0	1	2	3	4	5	6	7	8	9	10
4. Sleep	0	1	2	3	4	5	6	7	8	9	10
5. Mood	0	1	2	3	4	5	6	7	8	9	10
6. Concentration	0	1	2	3	4	5	6	7	8	9	10
7. Relations with others	0	1	2	3	4	5	6	7	8	9	10
8. Sexuality	0	1	2	3	4	5	6	7	8	9	10
9. Enjoyment of life	0	1	2	3	4	5	6	7	8	9	10
10. Overall quality of life	0	1	2	3	4	5	6	7	8	9	10

PATIENT HEALTH QUESTIONNAIRE (PHQ-9)

NAME: _____ **DATE:** _____

Over the last 2 weeks, how often have you been bothered by any of the following problems?
(use "✓" to indicate your answer)

	Not at all	Several days	More than half the days	Nearly every day
1. Little interest or pleasure in doing things	0	1	2	3
2. Feeling down, depressed, or hopeless	0	1	2	3
3. Trouble falling or staying asleep, or sleeping too much	0	1	2	3
4. Feeling tired or having little energy	0	1	2	3
5. Poor appetite or overeating	0	1	2	3
6. Feeling bad about yourself—or that you are a failure or have let yourself or your family down	0	1	2	3
7. Trouble concentrating on things, such as reading the newspaper or watching television	0	1	2	3
8. Moving or speaking so slowly that other people could have noticed. Or the opposite—being so fidgety or restless that you have been moving around a lot more than usual	0	1	2	3
9. Thoughts that you would be better off dead, or of hurting yourself	0	1	2	3

add columns + +

(Healthcare professional: For interpretation of TOTAL, please refer to accompanying scoring card). TOTAL:

10. If you checked off any problems, how difficult have these problems made it for you to do your work, take care of things at home, or get along with other people?	Not difficult at all	_____
	Somewhat difficult	_____
	Very difficult	_____
	Extremely difficult	_____

Attentional Functional Index

- I. At this time, how well do you feel you are functioning in each of the areas below?
Place a mark through the line at whatever point best describes how you are doing in each area at present.

1. Getting started on activities (tasks, jobs) you intend to do. Not at all _____ Extremely well
2. Following through on your plans. Not at all _____ Extremely well
3. Doing things that take time and effort. Not at all _____ Extremely well
4. Making your mind up about things. Not at all _____ Extremely well
5. Keeping your mind on what you are doing. Not at all _____ Extremely well
6. Remembering to do all the things you started out to do. Not at all _____ Extremely well
7. Keeping your mind on what others are saying. Not at all _____ Extremely well
8. Keeping yourself from saying or doing things you did not want to say or do. Not at all _____ Extremely well
9. Being patient with others. Not at all _____ Extremely well

- II. At this time, how would you rate yourself on:

10. How hard you find it to concentrate on details. Not at all _____ A great deal
11. How often you make mistakes on what you are doing. Not at all _____ A great deal
12. Forgetting to do important things. Not at all _____ A great deal
13. Getting easily annoyed or irritated. Not at all _____ A great deal

Exercise Pattern Assessment (Baseline):

8. What is your usual walking pace outdoors? Unable to walk eight blocks or climb a flight of stairs due to physical impairment.
 Easy, casual (less than 2 mph) Normal, average (2-2.9 mph) Brisk pace (3-3.9 mph) Very brisk/striding (4 mph or faster)

9. How many flights of stairs (not steps) do you climb daily? (Do not include time spent on stair or exercise machines.)
 No flights 1-2 flights 3-4 flights 5-9 flights 10-14 flights 15 or more flights

10. During the past year, what was your average total time per week at each activity?

	AVERAGE TOTAL TIME PER WEEK												
	NONE	1-4 Min.	5-19 Min.	20-29 Min.	40-80 Min.	1.5 Hrs.	2-3 Hrs.	4-6 Hrs.	7-10 Hrs.	11-20 Hrs.	21-30 Hrs.	31-40 Hrs.	40+ Hrs.
Walking to work or for exercise (including golf)													
Jogging (slower than 10 minutes/mile)													
Running (10 minutes/mile or faster)													
Bicycling (including stationary machine) Biking intensity:  Low  Medium  High													
Lap swimming Swimming intensity:  Low  Medium  High													
Tennis Tennis intensity:  Low  Medium  High													
Squash or racquetball													
Other aerobic exercise (exercise classes, etc.)													
Lower intensity exercise (yoga, stretching, toning)													
Moderate outdoor work (e.g., yardwork, gardening)													
Heavy outdoor work (e.g., digging, chopping)													
Weight training/resistance exercises (include machines such as LifeFitness)													
Standing or walking around work													
Standing or walking around home													
Sitting at work or commuting													
Sitting at home while watching TV/VCR/DVD													
Other sitting at home (e.g., desk, eating, computer)													

11. In an average week, on how many days do you usually exercise (include brisk walking or more strenuous activity)?
 None 1 day 2 days 3 days 4 days 5 days 6 days 7 days

Please record any exercise that you do for the seven consecutive days prior to your visit with exercise trainer.

Date	Day of Week	Time	Type of Activity	Duration (minutes)	Heart Rate	Perceived Intensity	Nausea/Fatigue (1-10 with 10 feeling great)	Comments
	MONDAY					 Light  Moderate  Vigorous	___ Nausea ___ Fatigue	
	TUESDAY					 Light  Moderate  Vigorous	___ Nausea ___ Fatigue	
	WEDNESDAY					 Light  Moderate  Vigorous	___ Nausea ___ Fatigue	
	THURSDAY					 Light  Moderate  Vigorous	___ Nausea ___ Fatigue	
	FRIDAY					 Light  Moderate  Vigorous	___ Nausea ___ Fatigue	
	SATURDAY					 Light  Moderate  Vigorous	___ Nausea ___ Fatigue	
	SUNDAY					 Light  Moderate  Vigorous	___ Nausea ___ Fatigue	

D:\Documents and Settings\cdj\My Desktop\CMCEExercise DAL.doc

EQ-8 Quotient

Please answer on a scale of 1-5 (1 disagree strongly; 5 agree completely) how well each statement matches your personality:

1. I find it easy to put myself in somebody else's shoes.
2. I am good at predicting how someone will feel.
3. I am quick to spot when someone in a group is feeling awkward or uncomfortable.
4. Other people tell me I am good at understanding how they are feeling and what they are thinking.
5. I find it hard to know what to do in a social situation.
6. I often find it hard to judge if something is rude or polite.
7. It is hard for me to see why some things upset people so much.
8. Other people often say that I am insensitive, though I don't always see why.

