3.2.2 Secondary Endpoints

Mean percent change from baseline to 12 months and patterns of change from baseline with respect to the following:

Metabolic Impact on Diabetes and Cardiovascular Disease Risk Factors:

- Fasting blood glucose
- Fasting plasma insulin level

- Insulin resistance as calculated by HOMA-IR
- Hemoglobin A1c
- Fasting lipids (total cholesterol, LDL, HDL, triglycerides)
- Waist circumference
- Body weight/body mass index
- Exercise patterns as measured by validated questionnaire and ambulatory accelerometer assessment (Appendices 2 and 5 respectively)
- Blood pressure

Bone Health:

- Bone density at the lumbar spine, femoral neck, and total hip as assessed by DXA scan among patients without bone metastases at the time of study entry
- Serum 25-(OH) vitamin D levels

Quality of Life/Psychosocial Impact:

- Depression as measured by PHQ-9
- Cognitive function as measured by Attentional Functional Index
- Overall quality of life as measured by SF-12
- Fatigue as measured by the Lee Fatigue Scale
- Erectile and urinary function as measured by EPIC-26
- Hot flash severity as measured by Hot Flash Related Daily Interference Scale

[figure not shown]
Patient Satisfaction:

- Patient satisfaction as measured by a validated questionnaire
- Patient insight and understanding of treatment and disease-related issues as measured by a self-administered assessment

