7.6 Every 3 Month Study Visits (+/- 2 weeks)

7.6.1 Clinical Assessment

- Physical exam
- Concomitant medications
- ECOG Performance Status
- Quality of life questionnaires
 - SF-12, EPIC-26, HFRDIS, Lee Fatigue Scale, PHQ-9, Attentional Functional Index, exercise pattern assessment, empathy scale

- Weight, body mass index, and percent body fat by bioimpedance measurement
- Patients will be referred to the Symptom Management Service, nutrition service, and/or exercise physiologist for further evaluation at the discretion of health care provider or per patient request (Standard-of-care treatment arm only)
- LHRH analogue administration
- Counseling regarding lifestyle modifications and review of the results of the above laboratory tests and quality of life questionnaires by a trained nurse practitioner or physician.
 - The PHQ-9 questionnaire screening for depression must be completed in person during the study visit and must be signed by treating health care provider prior to patient discharge from clinic

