7.7 End of Month 12 Study Visit (+/- 2 weeks)

7.7.1 Clinical Assessment

- Physical exam
- Concomitant medications
- ECOG Performance Status
- Quality of life questionnaires
 - SF-12, EPIC-26, HFRDIS, Lee Fatigue Scale, PHQ-9, Attentional Functional Index, empathy scale
- Weight, body mass index, and percent body fat by bioimpedance measurement

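### Item 10 of the exercise questionnaire recalls the past year but is due every 3 months, so its month 3, 6 and 9 values mix in pre-study time; the plan also contradicts itself on whether exercise is assessed at month 12

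*Combined protocol and SAP*

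**What the plan says.** Section 3.2.2 lists among the secondary endpoints "Exercise patterns as measured by validated questionnaire and ambulatory accelerometer assessment", to be compared as percentage change to month 12 and as a course over time. Section 9.8.2 analyses secondary endpoints across the time points with repeated-measures methods, so quarterly values enter a planned analysis.

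The form in Appendix 2 is headed "Exercise Pattern Assessment (Baseline)". Its grid of weekly time per activity, item 10, asks "During the past year, what was your average total time per week at each activity". Other items carry no past-year recall: item 8 asks "What is your usual walking pace outdoors", item 9 asks about stairs climbed daily, and item 11 asks "In an average week, on how many days do you usually exercise". A one-week log follows, with the instruction "Please record any exercise that you do for the seven consecutive days prior to your visit with exercise trainer".

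On timing, the 3-month list in Section 7.6.1 reads "SF-12, EPIC-26, HFRDIS, Lee Fatigue Scale, PHQ-9, Attentional Functional Index, exercise pattern assessment, empathy scale". The month-12 list in Section 7.7.1 reads "SF-12, EPIC-26, HFRDIS, Lee Fatigue Scale, PHQ-9, Attentional Functional Index, empathy scale". The Section 7.1 schedule marks the questionnaire row at month 12, and its footnote c counts the exercise questionnaires in that row. Section 8.2 has the Appendix 2 questionnaires completed at baseline and at 3-month intervals.

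**The concern.** A question about the past twelve months, asked every three months, cannot follow change from quarter to quarter. Until month 12 each answer is partly a report on life before enrolment. A repeated-measures analysis of those answers would describe the recall window as much as the patients' behaviour.

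This matters because Section 1.2.1 expects the clinic to act on body fat through sustained changes in diet and exercise. When and how far exercise changed, by arm, is what a reader will look for to interpret the body-fat result, whether positive or null.

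Two further points bear on the same endpoint. The two visit lists differ in one questionnaire, the exercise assessment, and it is missing at the visit that defines the endpoint. The one-week log, which has a suitably short recall, is tied to a visit that is routine in only one arm.

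**Working it through.** The plan gives no score, sample size or power for the exercise endpoint, so there is no stated figure to reproduce.

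**1. How much of the recall window is on study**

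Inputs: recall of 12 months (Appendix 2, item 10); assessments at months 3, 6, 9 and 12 (Sections 7.1, 7.6.1 and 8.2).

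At month m the on-study share is m/12 and the pre-study share is (12 − m)/12.

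**2. What item 10 would show**

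Assume the answer is a true 12-month average and that activity was steady in the year before enrolment.

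- *Step:* activity changes by D on Day 1 and stays there. Reported change = D × m/12.
- *Linear rise:* activity rises evenly to D at month 12, so its current level at month m is D × m/12. Averaging over the window, reported change = D × (m/12)² / 2.

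| Month | Pre-study share | Step: reported share of D | Rise: current level | Rise: reported share of D |
|---|---|---|---|---|
| 3 | 9/12 = 75% | 25% | 25% | 3.1% |
| 6 | 6/12 = 50% | 50% | 50% | 12.5% |
| 9 | 3/12 = 25% | 75% | 75% | 28.1% |
| 12 | 0% | 100% | 100% | 50% |

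Under the step, a change completed on Day 1 is reported as a straight climb over the year. Under the rise, the month-12 answer is the average of the study year, half the level then reached.

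**3. Differences between arms**

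Both arms have the same window, and randomisation balances pre-study activity in expectation. Under the step, the difference at month m is therefore the true difference times m/12. With an unchanged standard deviation, the sample size needed for the same power is multiplied by 1/(m/12)²: 16 at month 3, 4 at month 6, 1.8 at month 9 and 1 at month 12.

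**4. The month-12 contrast**

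The baseline answer covers the year before the study and the month-12 answer covers the study year. A visit two weeks early still gives 50/52 = 96% on-study time. The two windows hardly overlap, so this contrast works if the form is given at month 12.

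**5. Is it given at month 12?**

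- Section 7.1 with footnote c: yes.
- Section 8.2: yes, since month 12 falls on the 3-month cycle.
- Section 7.7.1: not listed, although the other questionnaires of Section 7.6.1 are.

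**6. The one-week log**

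The log precedes a visit with the exercise trainer. Section 7.1 footnote b and Section 7.5 give STAND patients four such visits on a rotating schedule. Usual-care patients see the trainer only on request or referral. The log as instructed therefore yields routine data in one arm and selected data in the other.

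**The case against.** The strongest reply is that the endpoint survives. Its named contrast is baseline to month 12, which item 10 can measure. Items 8, 9 and 11 can be repeated quarterly without this problem. The endpoint also has a device component with a seven-day wear period (Appendix 5). All of this stands, and it rules out several stronger readings that a reader might infer:

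- *That the exercise endpoint cannot measure change during STAND.* The documents do not support this. The recall problem is confined to item 10 at months 3, 6 and 9.
- *That interim differences between arms would be artefacts.* With a shared window they are attenuated, not created. It is the shape over time that is distorted.
- *That no month-12 exercise value is planned.* Two places call for it and one omits it. This is a contradiction to reconcile.
- *That the log replaces the form after baseline, leaving usual care without a comparator.* Nothing in the plan says so, and Section 7.6.1 schedules the assessment without limiting it to one arm. The narrower point is that the log could not serve as a comparable follow-up measure while it depends on trainer visits.
- *That no follow-up form exists.* None is visible, but the form as read starts at item 8 and the SF-12 appears only as headings, so content may have been lost. The baseline label may itself imply a companion form.

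The reply has limits. Walking pace, stairs and days per week do not replace activity time. The device has no row in the Section 7.1 schedule, its use is described only at the trainer visit (Section 7.5), and Section 9.7.2 names a pedometer instead. It is free of the recall problem, but its collection in usual care is not assured either.

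**Conclusion.** The point holds in a limited form. If the Appendix 2 form is repeated as scheduled, item 10 carries 75%, 50% and 25% pre-study time at months 3, 6 and 9, and the planned analysis of its course over time would be distorted accordingly. Baseline to month 12 remains valid as a comparison of the pre-study year with the study year. Sections 7.1 and 8.2 conflict with Section 7.7.1 on month 12; a site following only Section 7.7.1 would lose that value.

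The percentages rest on accurate 12-month averaging and on weekly time treated as continuous, although the grid records bands and the plan gives no scoring rule. The reported shares of change also depend on the assumed step or linear rise, and within an arm on steady pre-study activity. If a separate follow-up form with shorter recall exists, the quarterly dilution would not arise in this form, but baseline and follow-up would then use different recall periods.

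This concerns one secondary endpoint in a phase 2 study. It does not touch the body-fat analysis or the sample size. The correction is worth making because it is cheap.

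**What to change.** - Use one exercise form with one short recall period, for example *during the past 3 months*, in both arms at baseline and months 3, 6, 9 and 12. Drop the baseline label from its heading.
- Add the exercise pattern assessment to the Section 7.7.1 list so that it agrees with Section 7.1 and footnote c.
- If the one-week log is to supply endpoint data, uncouple it from the trainer visit and collect it at the same times in both arms.
- For item 10 answers already collected with past-year wording, analyse only baseline against month 12 and leave item 10 out of the quarterly analysis. Keep items 8, 9 and 11 in that analysis.

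The cost is one edited form and a few lines of protocol text, with no extra visit. The drawback is that shorter recall departs from the recall period printed on the form, which matters because the endpoint is described as using a validated questionnaire. The change should be stated when results are reported.
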